3.4 Selection of volunteers

Patients with heart disease undergoing cardiac surgery, monitored at the InCor outpatient clinic. Randomization will be performed 1:1 using an electronic randomization system and subsequently stratified from the RedCap platform, without knowledge by the team involved in the study. Patients will be randomized to intervention group (teleassisted group) or control group (standard follow-up of the institution)

1. **Control group (N=50):** patients with heart disease who underwent a surgical procedure with standard outpatient and post-surgical follow-up, according to institutional routines and protocols;
2. **Tele-assisted group (N=50):** patients with heart disease undergoing a surgical procedure remotely monitored through *smartwatch* and application.

Adult patients will be included, of both sexes, and ethnic profile representative of the Brazilian population, characteristic of the user population of the Unified Health System (SUS).

re-hospitalization rate, through scheduled consultations and extra interurrences (clock x institutional standard). As secondary outcomes will be evaluated: technological and treatment adherence, through the use of the mobile application by patients and development and implementation of the telemonitoring platform.

The goal is the inclusion of 40 patients/month (in all, in the 2 study groups: Remotely monitored watch group and group without a watch, following the institutional standard, following the randomization order generated by a specific

system) with 20 in each group of the study. In addition, the inclusion of patients will happen gradually and continuously, with 1 patient per group/working day.

Sem 1	Sem 2	Sem 3	Sem 4	Sem 5	Sem 6	Sem 7	Sem 8	Sem 9
1 ao 5	6 ao 10	11 ao 15	16 ao 20	21 ao 25	26 ao 30	31 ao 35	36 ao 40	41 ao 45
						1 ao 3	4 ao 8	9 ao 13
Sem 10	Sem 11	Sem 12	Sem 13	Sem 14	Sem 15	Sem 16	Sem 17	
46 ao 50								
14 ao 18	19 ao 23	24 ao 28	29 ao 33	34 ao 38	39 ao 43	44 ao 48	49 ao 50	
● Inclusão ● Retorno								

Figure 3. Flow of inclusion of patients in each arm of the study.

The remote patient monitoring flowchart to be used in this project is shown in Figure 3. Briefly, it includes:

1. Preoperative outpatient consultation with complete anamnesis to verify eligibility for using the **SAMSUNG™ Galaxy Watch5 Smartwatch**;
2. Hospitalization, surgery and collection of intraoperative data;
3. Training of the patient and/or family member responsible for the use of *smartwatch* and *smartphone* to start post-operative remote monitoring;
4. Upon hospital discharge, the patient will receive guidance for follow-up on the platform with the **Smartwatch SAMSUNG™ Galaxy Watch5** ;
5. Remote patient monitoring with **SAMSUNG™ Galaxy Watch5 Smartwatch** and app for 30 ± 3 days;
6. Monitoring by InCor's multidisciplinary team of the parameters collected using the **Smartwatch SAMSUNG™ Galaxy Watch5** and an application installed on a *smartphone*; identifying risks for early interventions in the face of any relevant intercurrentence;

7. Remote monitoring of the patient by teleconsultation, in case of detection of intercurrents. In cases considered serious by the clinical team, patients will be instructed to seek the InCor PS;
8. Face-to-face return to the outpatient clinic 30 ± 3 days after discharge for evaluation by the clinical team and conclusion of participation in the study.

Figure 4. Proposed flowchart for the project.

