3. METHODOLOGY

3.1 Place of study

This project will be carried out entirely on the premises of the Instituto do Coração of the Hospital das Clínicas of the Faculty of Medicine of the University of São Paulo. The sample will consist of 100 outpatients, with heart disease undergoing cardiac surgery, and selected during the pre -surgical consultation. The sample size was proposed by the contractor because it is a pilot study to evaluate the accuracy of the equipment in a sample with POAF.

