3.5 Data collection, clinical examinations and evaluation of results

In this project, wearable devices such as the Galaxy Watch will be used. 5 together with Galaxy series smartphones (A or S line) for the acquisition of blood pressure measurements, arterial hemoglobin oxygen saturation (SpO2), heart rate and ECG. This data will be transmitted to a repository, in a secure cloud environment, which meets the requirements of the General Data Protection Act

(LGPD) (Figure 5). In addition, data will be transmitted to a platform to be developed by InCor's IT team, as part of the project, and integrated into InCor's electronic medical record through the WebAdmin tool .

[figure not shown]

Figure 5 . Conceptual diagram for the Telemonitoring Platform.

The division of the study into phases and activities was carried out according to the table and description below.

Phase	Local	Activity
Phase 1	outpatient	
 • Inclusion of patients • Preoperative consultation; • Meeting with the project coordination team; • Complete anamnesis; • Application of the TCLE; • Collection of additional and contact information;
Level 2	hospitalization	
 • Hospitalization; • Eventually, some patients may be included in the study after hospitalization, prior to surgery, with the application of informed consent at this time;
phase 3	surgical	
 • Performing the surgical procedure; • Intraoperative data collection; • Postoperative evaluation and discharge • Patient guidelines; • Signature of the equipment loan liability term (smartphone and smartwatch); and the term for using data from the Electronic Health Record; • Calibration: 
 - BP, serial measurements - smartwatch SAMSUNG + traditional auscultatory method; - ECG - smartwatch SAMSUNG + traditional ECG; - SpO2 - SAMSUNG smartwatch oximetry + traditional oximetry; • Questionnaire of events observed during the remote phase;

Phase 4	remote collection	
 Tracking, monitoring and managing each participant's remote data collection for 30 ± 3 days; these being: 
 - Automatically collected: SpO2, heart rate, steps and sleep. - Collected manually: blood pressure and ECG. Telephone contact, teleconsultations, and unscheduled face-to-face consultations in cases of complications;

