	Detecção de FC > 100	Realizar medidas de parâmetros indiretos (ECG, P.A. E SPO ²)	Entrar em contato com a enfermeira informando o ocorrido	Orienta o paciente a procurar o PS do InCor
	PAS: Sistólica < 90 e > 180 mmHg	Realizar medidas de parâmetros indiretos (ECG, P.A. E SPO ²)	-	Orienta o paciente a procurar o PS do InCor
	PAS: Diastólica < 60 e > 110 mmHg	Realizar medidas de parâmetros indiretos (ECG, P.A. E SPO ²)	-	Orienta o paciente a procurar o PS do InCor
	PAS: Sistólica 140 - 180 mmHg	Realizar medidas de parâmetros indiretos (ECG, P.A. E SPO ²)	Entrar em contato com a enfermeira da equipe pelo telefone	Analisar os parâmetros clínicos e os sintomas do paciente. Enfermeira aciona teleconsulta com o médico se necessário. Em caso de necessidade, o médico orienta o paciente a procurar o PS do InCor
	PAS: Diastólica 90 - 110 mmHg	Realizar medidas de parâmetros indiretos (ECG, P.A. E SPO ²)	Entrar em contato com a enfermeira da equipe pelo telefone	Analisar os parâmetros clínicos e os sintomas do paciente. Enfermeira aciona teleconsulta com o médico se necessário. Em caso de necessidade, o médico orienta o paciente a procurar o PS do InCor
	SPO ² : 91 - 95%	Realizar medidas de parâmetros indiretos (ECG, P.A. E SPO ²)	Entrar em contato com a enfermeira da equipe pelo telefone	Analisar os parâmetros clínicos e os sintomas do paciente. Enfermeira aciona teleconsulta com o médico se necessário. Em caso de necessidade, o médico orienta o paciente a procurar o PS do InCor
	SPO ² : <90%	Realizar medidas de parâmetros indiretos (ECG, P.A. E SPO ²)	Entrar em contato com a enfermeira da equipe pelo telefone	Orienta o paciente a procurar o PS do InCor
	Sono: < 7 horas contínuas	N/A	Entrar em contato com a enfermeira da equipe pelo telefone	Analisa a possível causa e fornece orientação de Higiene do Sono
	Passos: <500 passos	N/A	Entrar em contato com a enfermeira da equipe pelo telefone	Analisa a possível causa e orienta o paciente a aumentar o nº de passos

Table 2. Flow of care for patients in the study (alerts, guidelines, interventions and actions)

The institutional electronic medical record (Si3) software modeling that will be used in the project to access clinical and functional information regarding patient data, are exemplified in the figures below:

Figure 6. Institutional Electronic Health Record: Macro view of the alerts referring to the teleassisted group .

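### The between-arm re-hospitalization comparison is open to differential ascertainment: the event is undefined, alert-driven referral exists only in the watch arm, and no common event capture is described

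*Combined protocol and SAP*

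**What the plan says.** Section 3.4 sets the between-arm comparison as the "re-hospitalization rate, through scheduled consultations and extra interurrences (clock x institutional standard". The opening of that sentence is not in the available text, so the outcome's rank cannot be read from it; the next sentence turns to secondary outcomes. Neither section 3.4 nor any other available section defines a re-hospitalization or fixes its counting window.

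Section 3.11 defines alerts for the teleassisted group. In its Table 2, four of the five red-range rows (heart rate above 100, systolic pressure, diastolic pressure, SpO2 below 90%) carry the action "Orienta o paciente a procurar o PS do InCor", that is, the patient is directed to the InCor emergency service. The row for heart rate below 50 and the milder blood pressure and SpO2 rows ask for telephone contact with the team nurse, with teleconsultation or referral if needed. Controls have institutional routine follow-up and no wearable.

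Table 1 in section 3.5 lists "Questionnaire of events observed during the remote phase" under Phase 3 (surgery and discharge). The remote phase is Phase 4, which lists "Telephone contact, teleconsultations, and unscheduled face-to-face consultations in cases of complications". Phase 5, the outpatient return, lists a quality-of-life and perception questionnaire but no event form.

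**The concern.** A randomised comparison of event rates needs the same event, looked for in the same way, in both arms. Here two things could separate the arms without any difference in how patients fare.

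- **Counting.** If an emergency visit prompted by an alert, with no admission, enters the rate, the watch arm gains events from a source the control arm does not have.
- **Detection.** Watch patients are observed daily for 30 ± 3 days, and the team learns of problems through the platform. For controls no matching step is described. The one form that asks about events of the period is placed before the period begins.

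Either mechanism would make the watch arm look worse, or hide a real benefit. A genuine admission that follows an alert is a different matter: it is part of what the intervention does and should count.

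**Working it through.** **Plan's own figure.** 50 + 50 = 100 patients. Section 3.1 says "The sample size was proposed by the contractor because it is a pilot study to evaluate the accuracy of the equipment" and gives no event rate, effect size or power, so there is no derivation to reproduce.

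**Step 1: the two arms side by side.**

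| | Watch arm | Control arm |
|---|---|---|
| Alerts | Yes (3.11) | None |
| Alert-driven emergency referral | Yes (Table 2) | None |
| Unscheduled contacts | Listed in Phase 4 | Possible in routine care; no recording step described |
| Day-30 return | Yes (3.4, item 8) | Not excluded; Figure 3 schedules returns for each arm |
| Event form at that return | None listed | None listed |

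**Step 2: inputs for the illustration.** From the documents: n = 50 per arm, allocated 1:1 (3.4). Section 3.6 sets p < 0.05, written for the comparison of the device with reference methods; no between-arm test is specified. Assumed here: a two-sided uncorrected chi-square test, a true re-hospitalization rate p equal in both arms, and a share q of otherwise event-free watch patients counted only because of an alert-driven visit.

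**Step 3: counting alert-only visits.** Observed watch rate = p + (1 − p)q. With p = 15%, this is 0.15 + 0.85q. The rejection rate comes from exact enumeration of two Binomial(50) arms, both directions added.

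| q | Watch arm reads | Control arm reads | Trials declaring a difference |
|---|---|---|---|
| 0 | 15.0% | 15% | 5.5% |
| 2% | 16.7% | 15% | 6% |
| 5% | 19.25% | 15% | 9% |
| 10% | 23.5% | 15% | 19% |
| 20% | 32.0% | 15% | 53% |
| 30% | 40.5% | 15% | 83% |

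The choice of p matters less than q. At q = 10% the rejection rate is about 26% for p = 10% (0.260 + 0.001) and about 16% for p = 20% (0.154 + 0.002). Fisher's exact test is more conservative: with p = 15% it gives about 13%, 44% and 77% at q = 10%, 20% and 30%.

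**Step 4: masking a benefit.** Suppose the watch truly halves the rate from 20% to 10%. At q = 10% the watch arm reads 0.10 + 0.90 × 0.10 = 19%, against 20% in controls, so the benefit all but disappears. At q = 20% it reads 0.10 + 0.90 × 0.20 = 28%, and the direction reverses.

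**Step 5: unequal detection alone.** Suppose only true admissions count, all are found in the watch arm, and a fraction s is found in controls. With p = 15%, s = 90% gives 0.15 × 0.9 = 13.5%, and a difference is declared in 6.0% of trials (0.044 + 0.017, before rounding 0.0604). With s = 80%, controls read 0.15 × 0.8 = 12%, and the figure is 7.8%. The reference is 5.5%.

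**Step 6: precision with ascertainment repaired.** Power for a true halving from 15% to 7.5% at 50 per arm is about 22%. If both arms are at 15%, the 95% interval for the difference is about ±1.96 × √(2 × 0.15 × 0.85 / 50) = ±14 percentage points.

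**The case against.** A reader might infer that the outcome is biased by design: that it counts contacts only the watch arm can have, and that its own questionnaire is mistimed. The documents do not support that much.

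- The wording in 3.4 may name the route by which readmissions are found. No section says that a call, a teleconsultation or a visit without admission is an event.
- Only alerts are confined to the watch arm. Controls can have unscheduled visits in routine care, and the day-30 return is not limited to one arm.
- Nothing links the Phase 3 questionnaire to re-hospitalization. It may be a misplaced row or a form handed out at discharge.
- Referral is not plainly automatic. Section 3.4, item 7, keeps it for cases the clinical team considers serious, and for milder readings Table 2 has the patient telephone the nurse.
- Other records exist. The closure form covers death, loss to follow-up and adverse events, the diary covers symptoms, and SI3 holds patients' care data.
- The large false-positive figures need every alert-driven visit to count, at rates the documents do not give.

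All of this stands, and it rules out a claim of demonstrated bias. It does not close the gap. If the wording means route of detection, detection is still described as continuous in one arm and routine in the other. SI3 is not named as the source of this outcome, and nothing describes how admissions to other hospitals are found. A form about the remote phase cannot be completed before that phase, whatever its purpose.

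**Conclusion.** The point holds as a risk of differential ascertainment, not as proven bias. It rests on three features of the text: no definition of the event, alert-driven referral in one arm only, and no common capture step, with the event questionnaire listed ahead of the period it covers.

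The size depends almost wholly on how visits without admission are counted. If they count, the distortion runs from negligible (q = 2%) to dominant (q = 20% or more). If they do not, under-capture of 10% to 20% of control events moves the false-positive rate by only about 0.5 to 2.3 points. These figures assume a 15% true rate, 50 per arm and a chi-square test that the plan does not specify.

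A reader might also infer that repairing this would let the trial settle whether telemonitoring changes re-hospitalization. It would not. This is an accuracy pilot, and 22% power for a halving leaves the comparison imprecise. The repair makes the pilot estimate interpretable. It should be made before enrolment, because control admissions elsewhere that nobody asked about cannot be reliably recovered later.

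**What to change.** - **Section 3.4:** define the between-arm outcome as unplanned inpatient admission to any hospital within 30 days of discharge. An alert-triggered admission counts like any other.
- **Section 3.4:** report emergency or unscheduled visits without admission separately by arm, split into alert-triggered and other.
- **Section 3.5, Table 1:** move the event questionnaire from Phase 3 to Phase 5 and give the same form to both arms. Because the return may fall from day 27 to day 33, record event dates so that both arms are cut at day 30. For patients seen before day 30 or not attending, complete the form by telephone.
- **Data source:** name one SI3 extraction, over the same 30-day window, for both arms.
- **Reporting:** give the difference with a confidence interval as a pilot estimate, not as a test of efficacy.

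The cost is protocol wording, one row moved in Table 1, one short form at a visit already planned, some telephone calls, and one extraction. The drawback is that fewer events count toward a comparison that is already imprecise. The alert and referral rules stay as they are.

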The postoperative period of cardiac surgery requires continuous observation from the health team, quick decision-making and highly complex care. This period presents many challenges for the multidisciplinary team, due to the need for intensive/constant monitoring and the potential postoperative complications. In addition to the lives lost, these postoperative complications dramatically increase hospital and healthcare costs ⁸.

One of the most frequent complications in the postoperative period of cardiovascular surgery are arrhythmias, with atrial fibrillation being the most frequent arrhythmia in the postoperative period ⁹. The prevalence of postoperative atrial fibrillation (POAF) varies between 15 and 40% in coronary artery bypass grafting procedures, 37 to 60% in valve surgery and more than 60% in combined interventions and 24% in patients undergoing heart transplantation.

In 90% of cases, POAF appears in the first four postoperative days ¹⁰. The average length of the first episode is 7-8 hours. Recurrence occurs in 40% of cases and occurs within the first 24 hours. Up to 80% of patients remain in sinus rhythm

24 hours after the first episode. About 14% of patients with atrial fibrillation after cardiac surgery (AFACS) remain with this rhythmic disorder for up to two weeks ¹¹.

Other emerging evidence suggests that POAF is associated with long-term sequelae such as stroke, heart failure, and all-cause ¹²mortality.¹³

Despite the advances in the area and the different methods for monitoring POAF, there is still no method that allows the automated evaluation of fibrillation episodes for a very prolonged period. Thus, the detection of POAF becomes an important challenge.

Wearable devices such as *smartphones* and *smartwatches*, are a great promise for screening and monitoring AF, and can present up to 93% sensitivity and 84% specificity when compared to standard ECG ¹⁴. In addition, they are easy to use and allow evaluating the possible adherence of patients to this new modality of assisted telemonitoring. However, to be used as a medical device, these *wearables* need to be accurate in outpatient settings.

Technological resources for health solution

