2. OBJECTIVES

2.1 Primary Purpose

telemonitoring platform using the **Smartwatch SAMSUNG™ Galaxy Watch5**, validating its applicability in patients with POAF.

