3.8 Provision and use of SAMSUNG devices (smartphone *and smartwatch*)

SAMSUNG devices will need to be handed over to participants in phase 3 of the study in order for remote data collection to begin. Volunteers must sign a loan liability term that guarantees the return of the device, and coverage in case of damage, as per Annex 3. Longitudinal data collection will be carried out for a period of 30 days \pm 3 days, requiring remote monitoring by team. Smartphones and *smartwatches* will be used to monitor adverse events regarding cardiac arrhythmia, heart rate *and* blood pressure. All devices will be delivered with the necessary applications for data collection duly installed. However, customization (login and initial settings) will be carried out by the Innovation team. During phase 4, each participant will remain with **SAMSUNG** devices for 30 days \pm 3 consecutive days. Participants must use the *smartwatch* and *smartphone* throughout the day, including while sleeping, and charge the equipment batteries regularly. The data will be collected by an application embedded in the equipment.

During phase 5, the participant must return to InCor for a final consultation of the study, and return of borrowed equipment.

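### Watch monitoring begins at discharge, probably after most POAF has started, and patients with POAF are not identified in the data, so the POAF conclusion needs narrowing and in-hospital POAF needs recording

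*Combined protocol and SAP*

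**What the plan says.** **Start and end of monitoring.** In the section 3.4 flowchart, training follows surgery, and then "Upon hospital discharge, the patient will receive guidance for follow-up on the platform with the" Samsung watch. Remote monitoring runs for 30 ± 3 days and closes with "Face-to-face return to the outpatient clinic 30 ± 3 days after discharge". Section 3.8 (provision of devices) agrees: "SAMSUNG devices will need to be handed over to participants in phase 3 of the study in order for remote data collection to begin". The loan term in Annex 5.2 covers 30 to 33 days from signature.

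**Target.** The readable part of section 2.1 describes a telemonitoring platform, "validating its applicability in patients with POAF". Section 3.1 justifies the sample of 100 as a pilot of device accuracy in a POAF sample.

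**Natural history (Introduction).** "In 90% of cases, POAF appears in the first four postoperative days". The first episode lasts 7-8 hours on average. "Recurrence occurs in 40% of cases and occurs within the first 24 hours". "Up to 80% of patients remain in sinus rhythm" a day after the first episode, and about 14% stay in AF for up to two weeks. Prevalence "varies between 15 and 40% in coronary artery bypass grafting procedures, 37 to 60% in valve surgery", and is above 60% in combined procedures.

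**Other relevant text.** Section 3.2 does not require POAF. Section 3.3 excludes stays of more than 14 days after surgery, but no usual or minimum discharge day is given. Table 1 (section 3.5) places a paired watch and traditional ECG in phase 3, and makes ECG capture manual in the remote phase. The rhythm field in the readable case report form (Annex 5.1) belongs to Visit 1, before surgery.

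**The concern.** The recording window and the disease window are anchored to different events. Recording is anchored to discharge and POAF to surgery. The longer the stay, the less POAF is left to observe.

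Two consequences follow. First, the monitored data may hold only a handful of patients in AF, too few to say much about how the platform or the watch performs in POAF. Few AF detections would then partly reflect when recording began, yet could be reported as a finding about POAF. Second, nothing visible in the data collection marks who had POAF during the stay. Results could therefore not be reported for the population that section 2.1 names, even if enough such patients were enrolled.

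**Working it through.** **The plan's own figure.** The total of 100 (50 per arm) comes without an event rate, power or precision target, so there is no calculation to reproduce. The check below uses expected counts.

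**Inputs.** Watch arm n = 50 (section 3.4). From the Introduction: prevalence p = 15%, 40% and 60%; share of first onsets after day 4 = 10% (100% − 90%); persistence = 14%. Discharge after day 4 is an assumption.

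**Formulas.**
- POAF cases: 50 × p.
- First onset under monitoring: 50 × p × 0.10. This is a ceiling, because some late onsets will still precede a later discharge.
- Any AF under monitoring, counting every persistent early case: 50 × p × (0.10 + 0.90 × 0.14) = 50 × p × 0.226.
- Chance that no watch patient has a late onset: (1 − 0.10p)^50.

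| p | POAF cases | Late onsets | Late onsets plus persistent | Chance of no late onset |
|---|---|---|---|---|
| 15% | 7.5 | 0.75 | 1.7 | 47% |
| 40% | 20 | 2.0 | 4.5 | 13% |
| 60% | 30 | 3.0 | 6.8 | 4.5% |

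The chance of five or more late onsets is 0.1%, 4.9% and 17.9% respectively.

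**Sensitivity to persistence.** Counting all of the 14% as still in AF at discharge is generous for a long stay, since that figure covers durations of up to two weeks. For a discharge soon after day 4 it may be slightly low: if up to 80% are in sinus rhythm at 24 hours, at least 20% are not. Using 20% gives 0.10 + 0.90 × 0.20 = 28%, or 2.1, 5.6 and 8.4 patients. Most POAF patients would still show no AF in the window.

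**Sensitivity to discharge day.** Spread the 90% evenly over days 1-4 (assumption). The share of onsets after discharge at the end of day d is 1 − 0.90 × d/4:
- day 1: 77.5%
- day 2: 55%
- day 3: 32.5%
- day 4: 10%, and no more than that later

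Most onsets precede monitoring for discharge from day 3 on, but not for discharge on day 2 or earlier.

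**What such counts can show.** Exact 95% intervals for patient-level sensitivity, as illustration:
- 3 of 3 detected: 29% to 100%
- 7 of 7 detected: 59% to 100%

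If recording covered the whole postoperative period and detection were near the 93% quoted in the Introduction:
- 19 of 20 detected: 75% to 99.9%
- 28 of 30 detected: 78% to 99%

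**Identification of POAF.** Section 3.2 does not select on POAF. The phase 3 paired ECG is a single resting comparison, so it shows AF only if AF is present at that moment. No in-hospital POAF variable is visible in Annex 5.1.

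**The case against.** The strongest reply is that post-discharge telemonitoring is the design. The Introduction argues for faster dehospitalization with remote follow-up and names prolonged rhythm evaluation as the gap. Section 3.4 lists re-hospitalization and platform implementation among its outcomes. Re-hospitalization cannot occur before discharge, so a window starting there is coherent. This stands, and it confines the problem to the POAF clause of 2.1 and the rhythm-accuracy aim.

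A reader might infer four stronger things that the documents do not support.

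- *That at least 90% of onsets certainly precede monitoring.* No discharge day is stated, so the figure holds only for discharge after day 4. The inclusion chart in section 3.4 shows week-1 patients first returning in week 7. Six weeks is 42 days, and 42 − 30 leaves about 12 days between inclusion and discharge. That span includes preoperative time, so it does not settle the length of stay.
- *That the window contains essentially no AF and the platform cannot be tested.* Late and persistent cases together give 1.7 to 6.8 expected patients, and more if combined procedures (above 60%) are common.
- *That a low AF alert count would mislead.* Section 3.11 and Table 2 define alerts for blood pressure, heart rate, oxygen saturation, sleep and steps. The readable text defines no AF or rhythm alert.
- *That rhythm during the stay goes unrecorded.* The printed form also lacks intraoperative and phase 5 fields that Table 1 plans to collect, so a missing field proves little. Watch patients have a phase 3 ECG with a cardiologist's report, and the institutional record exists. What stands is that no explicit in-hospital POAF variable is listed for either arm.

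**Conclusion.** The mismatch is real and follows from the protocol's own figures. If discharge comes after day 4, at most 10% of first POAF onsets fall under monitoring (0.75 to 3 of 50 watch patients). On the 14% persistence figure, about 23% of POAF patients (1.7 to 6.8) would show AF there. These figures rest on the Introduction's prevalence, timing and persistence and on an unstated discharge day. If onsets are even over days 1-4, most still precede monitoring for discharge from day 3 on.

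The monitored data would then contain few AF cases, and the patients with POAF named in 2.1 would not be identified. As written, a conclusion about applicability in POAF would not be supported. Platform feasibility and the re-hospitalization comparison are not affected.

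**What to change.** 1. **Record and report POAF status.** Take in-hospital POAF (onset and end dates) and rhythm at discharge from SI3, the institutional electronic record, in both arms. Report platform and rhythm results separately for patients with and without in-hospital POAF.
2. **Narrow the claim.** Reword the POAF clause of 2.1, and the planned conclusion, as AF persisting, recurring or newly arising after discharge. State the expected discharge day and the expected number of such cases in the watch arm.

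**Cost.** A protocol amendment and two or three fields filled from the existing record. Table 1 lists a signed term for use of record data beside the equipment loan, so confirm that it also covers control patients. The subgroups will be small, so results should be given as counts with intervals. The stated conclusion becomes narrower.

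**Optional, and not needed for the fix.** Starting the watch on the ward would move recording closer to the onset window. However, ward days plus 30 ± 3 days after discharge would in general exceed the 30 to 33 day loan term, which would have to be extended. It would also need more devices: about 1 per working day × 5 working days = 5, if the ward period were 5 working days (assumption). Some watches would go to patients later excluded for a stay beyond 14 days. The gain would be small while ECG is taken manually.
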